#### **Trial Flow Diagram:**

Trial	TB-DILI Trial	Protocol	1.2	date:	02-Aug-2022	Page 11 of 58
name:		version:				

# 1 Background and Rationale

## 1.1. Background

In 2018, 4,655 people were diagnosed with tuberculosis (TB) in the UK, equivalent to a rate of TB of 8.3 per 100,000 population. This was the lowest recorded rate of TB in the UK for the last 10 years. People born outside the UK accounted for 72% of notifications in 2018. The proportion of people with drug-sensitive TB who completed treatment by 12 months was 84.7% in 2017; in addition, 5.3% died and 4.2% were lost to follow up. Only 2.7% of people with TB were coinfected with HIV in 2018; most (81.7%) were born outside the UK. Early data from 2019 suggests that the rate of TB may be higher in 2019 compared to 2018.

The standard treatment of drug-sensitive TB involves a 4-drug combination of anti-TB therapy (ATT) for 2 months (intensive phase of treatment), followed by a 2-drug combination for 4 months (continuation phase of treatment), making a total treatment duration of 6 months. Cure rates are around 97%.9

Drug-induced liver injury (DILI) is the commonest serious adverse effect of ATT. DILI may result from direct toxicity of the primary compound or an immunological response to one or more of the drugs. Unpredictable or idiosyncratic reactions which develop acutely account for most types of DILI. These reactions are unpredictable based on the pharmacological action of the drug, independent of drug dose and are relatively unusual for each drug.

Among those who develop DILI on ATT, 16% develop jaundice and 5.3% acute liver failure; the latter is the most severe outcome of DILI, of which 22% can be fatal. Most patients with DILI who report symptoms experience nausea, vomiting, anorexia and lethargy. Early detection of DILI with cessation of the inciting drug(s) serves to limit the severity of DILI and its consequences. Not all asymptomatic increases in liver enzymes while on ATT constitute DILI episodes. Some of the increase in liver enzymes are self-limiting or are attenuated through a process called hepatic adaptation (please see later). However, very high levels of liver enzymes (>5x upper limit of normal) in the absence of symptoms are thought to represent early DILI episodes that, if left untreated (ie. continued exposure to the inciting drug(s)), would progress to symptomatic DILI.

Apart from any symptoms and sequelae related to DILI, a patient who experiences a DILI episode also suffers delay in the treatment of their primary illness. When a patient with active TB has a DILI episode, the overarching strategy is to i) stop the inciting drug(s), ii) allow the liver to recover and then iii) reintroduce as many first-line ATT drugs as possible to enable the highest chance of clinical cure of TB disease in the shortest length of time. The median duration of cessation of ATT is 18 days while reintroduction of ATT drugs takes a further 10 -14 days (median).2,12 Therefore, for each episode of DILI, a total of 28 days' delay can be expected before full ATT is re-started.12

Guiding the patient through recovery from DILI and re-establishment of ATT requires additional healthcare resources. In one study from Canada, 29 of 37 patients who developed serious ATT-related side effects made a total of 91 extra clinic visits, and the TB clinic nurses made an additional 30 home visits to 8 of these patients. If full standard first-line ATT is not reintroduced following DILI, modified regimens may require extension of the treatment duration beyond 6 months to achieve acceptable rates of clinical cure. This adds to patient and healthcare costs.

Trial	TB-DILI Trial	Protocol	1.2	date:	02-Aug-2022	Page 16 of 58
name:		version:				

Globally, rates of DILI following TB therapy of 2 - 25% are reported .14-18 In 2 UK studies, DILI was reported in about 7% of persons treated for TB; however, the definition of DILI differed between these studies.12,19

Roughly 53 - 57% of DILI episodes occur during the first 2 weeks of ATT, and 75 - 88% within the first 8 weeks, corresponding to the intensive phase of ATT.12,19-21

Our understanding of the differences in risk of DILI associated with individual ATT drugs comes from a range of studies including case-control studies, observational cohort studies, and clinical intervention trials. Most intervention trials have been designed primarily to test the efficacy of different ATT regimens with DILI measured as part of safety reporting (adverse events). DILI rates in efficacy trials have sometimes been noted to be lower than those observed under routine TB programmatic conditions and may reflect patients at higher risk of adverse effects not being recruited to intervention trials. Of the four standard first-line ATT drugs, ethambutol (E) very rarely causes DILI. Concerns centre mainly around isoniazid (H), rifampicin(R) and pyrazinamide (Z).

**Isoniazid (H).** Based on studies of the treatment of patients with latent TB infection (LTBI) where isoniazid was used as monotherapy for 6 to 9 months, H-related DILI occurred in 0.1% to 1% of cases.  In the REMOX trial (treatment for active TB), a H-free regimen had a numerically lower rate of DILI (2.2% versus 3.4%) than either the standard HRZE regimen or one where ethambutol (E) was replaced by moxifloxacin15, suggesting that the independent contribution of isoniazid to DILI during multi-drug therapy may be similar to or slightly higher than that suggested by the data in LTBI studies.

**Rifampicin (R).** Based on studies of the treatment of patients with LTBI where rifampicin (R) was used as monotherapy or in combination with isoniazid (RH), DILI occurred in 0.3% to 0.4% of cases, and in general, no more frequently than for patients treated with H alone. In two dose-ranging studies of rifampicin given as part of multidrug therapy for active TB, DILI occurred in up to 2% of participants at the standard 10 mg/kg dose, though data were not available on which drugs were implicated. Hepatotoxicity did not appear to be dose-related, supporting an idiosyncratic aetiology.

**Pyrazinamide (Z).** The projected difference in event rates between groups (Z-containing vs non-Z-containing reintroduction regimens) rests on the premise that pyrazinamide poses a higher risk of DILI than other first-line ATT drugs. There is no evidence to suggest that hepatic adaptation (the process that permits the safe reintroduction of drugs following a DILI event, discussed in more detail below) occurs to different degrees for different ATT drugs. Therefore, our estimates for the event rate in both randomised groups are based predominantly on data from studies that have compared DILI event rates between different ATT drugs.

Following recovery from an episode of DILI, reintroduction (re-challenge) of ATT drugs is safe for most patients. This is due to a process called **hepatic adaptation.** Hepatic adaptation after DILI might allow 75% - 90% of patients to be re-challenged with the same drugs, and ultimately continue taking these drugs.2,3 Initial description of this phenomenon involved 218 patients receiving isoniazid for latent TB; 20% developed raised liver enzymes including 3 with elevated bilirubin and despite continuation of the drug, none developed liver failure.28,29 The mechanism for hepatic adaptation is not fully known.30 In terms of recurrence of DILI due to all drugs after re-challenge, a systematic review did not show any significant difference between those who have recurrence of DILI (called positive re-challenge) and those who do not (negative re-challenge) which can effectively stratify patients based on risk of recurrent DILI.31 There is no evidence that severity of original DILI and recurrence of DILI are correlated.31

Trial	TB-DILI Trial	Protocol	1.2	date:	02-Aug-2022	Page 17 of 58
name:		version:				

We are aware of only 2 intervention trials that address the issue of ATT reintroduction following DILI.

- Sharma et al was a 3-arm trial (n= 175) designed to test different modes of reintroduction. All 3 regimens in the trial contained pyrazinamide (HRZ regimens). Patients aged >65 years were excluded because the authors felt the risk of DILI was increased in those who are older. Although point-estimates for DILI recurrence rates differed slightly across the 3 arms (13.8%, 10.2% and 8.6%), 95% confidence intervals (CIs) for between group effects were wide and provided no strong evidence in favour of any regimen.
- Tahaoglu et al was a 2-arm trial (n=45) designed to test reintroduction of a Z-containing versus non-Z-containing regimen (EHRZ vs EHR + Streptomycin). There was no age restriction for enrolment. DILI recurrence in the Z-containing arm was 25% (95% CI 9 to 45%) vs 0% in the non-Z containing arm. In addition, post-trial, all patients who had experienced DILI recurrence (all in the Z-containing arm) were safely re-challenged with the non-Z regimen. The authors interpreted this as further evidence of Z-related DILI. Of these 2 trials, only *Tahaoglu et al* provides data on Z vs non-Z regimens but it is limited by the small sample size. Nevertheless, the lower bounds of the event rate for the Z-containing regimen is similar to the overall event rate reported by *Sharma et al* (~10%) and is consistent with the observation that patients at higher risk of DILI were not enrolled by *Sharma et al*.

Four retrospective cohort studies report DILI recurrence frequencies following ATT reintroduction. It is very difficult to compare across these studies due to variations in a) patient cohorts, b) definitions of DILI used and c) methods for detection of DILI. *Costiniuk et al* (2015) studied 53 individuals with ATT-DILI (48 HIV co-infected). DILI recurrence occurred in 12% of the cohort; no association was observed with the mode of reintroduction (sequential (n=12) vs parallel (n=30)). *Natarajan et al* (2016) reported results in a conference abstract concerning 50 patients with DILI in whom HRZ was reintroduced with 10% DILI recurrence. *Abbara et al* (2017) described 105 patients with ATT-DILI, using a less strict definition of *possible DILI*. A non-Z regimen was reintroduced in all patients with 12.4% recurrence of *possible DILI*. Shamaei et al (2017) reported on 135 patients with ATT-DILI; 109 (80.7%) were re-challenged with a non-Z regimen and 26 (19.2%) with a Z-containing regimen. Patients in the non-Z group were highly selected for an increased risk of potential DILI (eg. 12.6% HIV positive vs 0%; viral hepatitis 11.4% vs 3.8%). DILI recurrence rates for non-Z vs Z-containing regimens were 17.4% vs 15.4% respectively).

# 1.2. Trial Rationale

In the National Health Service (NHS), the management of ATT-induced DILI is informed by both the NICE TB Guideline and the American Thoracic Society TB Guideline.8,9

The NICE TB Guideline (2016), section 1.7.4.1, recommends clinicians "sequentially reintroduce each of the anti-TB drugs at full dose over a period of no more than 10 days, starting with ethambutol and either isoniazid (with pyridoxine) or rifampicin." The NICE Guideline Development Group (GDG) acknowledged that the evidence supporting this recommendation was of very low quality; based on 2 trials (Sharma *et al.*, 2010, and Tahaoglu *et al.*, 2001). The recommendation was mainly developed by expert consensus.

The American TB Guideline (2006) also recommends sequential reintroduction of ATT; beginning with rifampicin (with or without ethambutol), then adding isoniazid after 3 to 7 days. In addition, it recommends *"For those who have experienced prolonged or severe hepatotoxicity, but tolerate reintroduction with rifampicin and isoniazid, rechallenge with pyrazinamide may be hazardous. In this circumstance, pyrazinamide may be permanently discontinued, with treatment extended to 9 months.* 

Trial	TB-DILI Trial	Protocol	1.2	date:	02-Aug-2022	Page 18 of 58
name:		version:				

Although pyrazinamide can be reintroduced in some milder cases of hepatotoxicity, the benefit of a shorter treatment course likely does not outweigh the risk of severe hepatotoxicity from pyrazinamide rechallenge."

These two Guidelines are interpreted variously by clinicians, in the NHS and globally, resulting in a range of clinical practice. Some clinicians prefer to routinely avoid reintroducing pyrazinamide (Z), aiming instead for a 9-month non-Z containing regimen. Others consider the severity of DILI in deciding on reintroduction of Z; however, the threshold for classifying 'milder DILI' also varies. It is equally difficult for patients to make informed choices. There are no data on patient-related costs or quality of life (QoL) measures to inform the balance between risk of recurrent DILI versus extension of treatment duration.

# **1.2.1.** Justification for participant population

The target population comprises of adults treated within the NHS for active TB with standard 4-drug ATT who have experienced an episode of DILI requiring these drugs to be stopped.

The main trial will determine the risk of recurrence and health economic impacts of a pyrazinamide (Z)-containing versus non-Z containing reintroduction regime following a DILI episode. Pyrazinamide (Z) is not a component of treatment for latent TB infection (LTBI). Therefore, including patients with LTBI in the main trial is not appropriate. Furthermore, anecdotal evidence suggests DILI occurrence (from treatment with R or H) in these patients, who are usually clinically well, is likely very low (<1.5%). A separate clinical trial to determine the safest and most effective drug reintroduction strategy in these patients is not feasible in the UK because of the very large sample size needed for a definitive study. Instead, we propose a cohort study to provide firmer estimates of the frequency of DILI occurrence and recurrence, and the quality-of-life impacts arising. The cohort study involving patients with latent TB infection (LTBI) will also benefit the current trial because it will keep sites actively recruiting into the programme of research. We provide further details of the cohort study in Appendix A.

# 1.2.2. Justification for design

This trial will provide reliable data on DILI recurrence rates and QoL for the 2 main reintroduction options in current practice in the NHS. These data will enable patients and their clinicians to make informed choices regarding the most appropriate strategy to adopt. We anticipate results from this trial to directly inform future clinical practice within the NHS and globally.

# 1.2.3. Choice of treatment

Both regimens are accepted as standard of care in the NHS and globally. Based on weak evidence, one regimen may be associated with a lower DILI recurrence frequency but entails a longer total duration of treatment (9 months vs 6 months).

# 1.2.4. Cohort Study: Patients with LTBI

Patients with LTBI who develop DILI while on anti-LTBI drugs comprise a separate target population. They will be approached to participate in a prospective observational cohort study. See Appendix A for full details of this cohort study.

Trial	TB-DILI Trial	Protocol	1.2	date:	02-Aug-2022	Page 19 of 58
name:		version:				

# 2. Aims, Objectives and Outcome Measures

# 2.1. Aims

To compare the relative safety and effectiveness, including cost, of two different drug reintroduction strategies in adults with TB following an episode of anti-TB DILI.

## 2.2. Objectives and outcome measures

#### 2.2.1. Primary

• DILI recurrence within 12 months following randomisation.

## 2.2.2. Secondary

- Severity of DILI recurrence
- Reported clinical cure at end of treatment (EoT)
- Reported clinical cure at 12 months
- Total number of days on ATT at EoT
- ATT adherence at EoT
- Adverse event rate at 12 months
- Mortality at 12 months
- Quality of Life using EQ-5D and healthcare resource use

# 3. Trial Design and Setting

#### 3.1. Trial Design

Phase III, multi-centre, randomised, open-label, parallel group, superiority trial with concealed allocation (1:1) and minimisation to receive either the intervention, sequential full-dose reintroduction of non-Z-containing 3-drug ATT (compromising EHR) or the control sequential full-dose reintroduction of a Z-containing 4-drug ATT (comprising EHRZ).

#### 3.2. Trial Setting

Patients will be recruited through secondary NHS TB centres across the UK. It is anticipated that at least 40 recruiting sites will be required to achieve the target sample size during a recruitment period lasting 48 months.

Potentially eligible patients will generally be identified in the following ways:

- 1. During routine outpatient clinics/consultations
- 2. Community clinics and mobile clinics
- 3. Hospital in-patients

Trial	TB-DILI Trial	Protocol	1.2	date:	02-Aug-2022	Page 20 of 58
name:		version:				

In light of the COVID-19 pandemic and revisions being made to clinical pathways within the NHS, it is expected that some routine clinic appointments may be carried out remotely via telephone/video call in place of a face-to-face visit. However, no major changes in the care pathway of patients who develop DILI are expected.

# 4. Eligibility

Potential participants will be identified at the time of DILI occurrence by the site PI and TB team. During the DILI recovery period (median 18 days from cessation of ATT drugs)12, eligibility screening, recruitment and randomisation will be carried out by research staff. Patients who require alternative 'bridging' TB drugs *during DILI recovery* will be eligible for trial participation. Only patients who are deemed suitable for reintroduction of standard 4-drug ATT after recovery from DILI will be enrolled and randomised.

In order to take part in the TB-DILI trial, patients must meet all of the listed inclusion criteria and none of the exclusion criteria at this baseline visit.

# 4.1. Inclusion Criteria

- Adult aged ≥18 years
- Experienced DILI with standard 4-drug ATT for active pulmonary or extra-pulmonary TB
- Medically suitable for re-introduction of standard 4-drug ATT

# 4.2. Exclusion Criteria

- Requirement for alternative ATT
- Unable to provide written informed consent

To obtain a realistic estimate of safety and tolerability, no adult will be excluded on the basis of (older) age, liver disease, alcohol use, HIV status or other medication use.

The NICE TB Guideline does not outline a specific LFT monitoring plan. Participating sites will be encouraged to adopt a preferred monitoring plan with flexibility for local practice variations across hospitals. Sites will be requested to upload all LFTs performed onto the eCRF.

**Definition of DILI**. This will be based on internationally recognised criteria that take into account baseline measurements.

Table 1. Clinical chemistry criteria for DILI in those with normal liver enzymes at baseline.

Any one of the following-

- >3-fold elevation in ALT and either bilirubin elevation exceeding 2 x upper limit of normal (ULN) or presence of hepatitis symptoms (anorexia, nausea, vomiting, abdominal pain)
- >5-fold elevation above ULN of alanine aminotransferase (ALT)
- >2-fold elevation above the ULN for alkaline phosphatase (ALP), particularly with accompanying 5'-nucleotidase or gamma-glutamyl transpeptidase (GGT) elevations and when there is no known bone pathology driving the rise in ALP.

Isolated hyperbilirubinemia or raised GGT in the absence of other liver enzyme elevations will not qualify as DILI. These case definitions are in agreement with those from the American Thoracic Society TB Guideline, but also include a cholestatic pattern of DILI (with elevation of ALP) which is observed in

ſ	Trial	TB-DILI Trial	Protocol	1.2	date:	02-Aug-2022	Page 21 of 58
	name:		version:				

up to 17% of ATT DILI cases. Case definitions for DILI in patients who have elevations of ALT or ALP  $\leq$  1.5 x ULN prior to the onset of ATT would be the same as those with normal ALT or ALP at the onset of ATT. In patients with ALT or ALP elevation  $\geq$  1.5 x ULN prior to ATT, it is important to distinguish natural fluctuations in ALT/ALP levels from DILI. For the TB-DILI trial, the following will apply:

in patients with ALT or ALP elevations  $\geq$ 1.5 x ULN prior to ATT, DILI will be defined as

- ALT  $\geq$ 3 x upper limit of baseline levels or
- ≥ 300 U/L or
- ALP  $\ge$  2 x upper limit of baseline,

irrespective of bilirubin elevation or hepatitis symptoms.

(criteria based on consensus guideline for the management of patients with chronic liver disease).

**Severity of DILI** will be graded according to the international expert working group as shown in Table 2.

Category	Severity	Description
1	Mild	Elevated ALT/ALP reaching criteria for DILI but bilirubin <2x ULN
2	Moderate	Elevated ALT/ALP reaching criteria for DILI and bilirubin $\ge 2x$ ULN
		or symptomatic hepatitis
3	Severe	Elevated ALT/ALP reaching criteria for DILI and bilirubin $\ge 2x$ ULN
		and one of the following:
		
 
International Normalised Ratio (INR) ≥1.5
 

		
 
ascites and/or encephalopathy, disease duration <26
 

		weeks, and absence of underlying cirrhosis 
		
 
Other organ failure considered due to DILI
 

4	Fatal or	Death or transplantation due to DILI
	transplantation	

Table 2. DILI Severity scale

# Definition of Recovery from DILI:

- 1) in those who had normal baseline LFTs return of liver enzymes to less than 2 x ULN ALT plus bilirubin in normal range,
- 2) in those who had elevated baseline LFTs either i) return of liver enzymes to less than 2X ULN ALT plus bilirubin in normal range or, ii) return to baseline levels, whichever is the greater; *PLUS* resolution of signs and symptoms of hepatotoxicity after withdrawal of ATT drugs (criteria based on the American Thoracic Society TB Guideline and NICE TB Guideline).

**Hepatic Adjudication Panel.** Liver enzyme elevation in isolation is not a sufficient criterion to confirm a diagnosis of DILI. Other factors to consider are i) temporal association of ATT with elevation of liver tests, and ii) exclusion of alternative explanations.

A blinded Hepatic Adjudication Panel will review all relevant data relating to possible DILI episodes. The panel will judge the probability of ATT-related DILI and DILI severity according to defined criteria. Differences will be resolved by consensus, with the option of co-opting a third panel member as needed.

ſ	Trial	TB-DILI Trial	Protocol	1.2	date:	02-Aug-2022	Page 22 of 58
	name:		version:				

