#### 6.3. Blinding and concealment

Allocation will be concealed to trial staff prior to randomisation using REDCap, an automated web system operated by the NCTU.

Blinding of the participants and site research team following randomisation is not possible due to the nature of the interventions.

Table 3 provides an overview of the blinding status of all individuals involved in the management and delivery of the trial.

Trial role	Blinding status	Comments
Participant	Not blinded	Not possible due to the nature of the intervention.
		Participants will be informed
		which arm of the trial they
		have been randomised to
		immediately after
		randomisation.

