#### Table 3: The blinding status of individuals involved in the trial

Trial	TB-DILI Trial	Protocol	1.2	date:	02-Aug-2022	Page 26 of 58
name:		version:				

Trial role	Blinding status	Comments
Principal investigator and site research staff	Not blinded	Not possible due to the nature of the intervention. Following randomisation, an e-mail will be sent to the PI (unblinded for participants they PI randomise only) and/or member of the site research team performing the randomisation (as delegated) confirming treatment
Chief Investigators	Blinded	allocation.The Chief investigator and Deputy Chief investigator will remain blinded to treatment allocation overall (knowledge of treatment allocation is limited to participants at their own site). In instances where serious adverse events are reported, the CIs will become unblinded to complete the full causality assessment.
Adjudication Panel	Blinded	The adjudication panel will remain blinded to treatment allocation overall when performing adjudication for a potential DILI during various timepoints within the trial.
Software programmer	Not blinded	The software programmer is responsible for the management of the randomisation system and database and will have access to all unblinded datasets within both systems.
TB-DILI Trial Management staff within NCTU	Not blinded	
 
Blinding of trial Management staff within NCTU impractical due to the range of potentially unblinding data collected during the trial.
 
For example, Serious Adverse Event reports will be handled by the trial management team who may become unblinded to a participant's treatment allocation.
 

ſ	Trial	TB-DILI Trial	Protocol	1.2	date:	02-Aug-2022	Page 27 of 58
	name:		version:				

Blinding status Not blinded	Data management staff will
	have access to the unblinded
	datasets within the trial
	randomisation system and
	database to ensure data
	quality and undertake central
	monitoring activities.
Not Blinded	The trial statistician will
	remain blinded (they will not
	have access to treatment
	allocations or data which has
	the potential to unblind) prior
	to approval of the statistician
	analysis plan. After approval of
	the analysis plan the trial
	statistician will be able to
	access potentially unblinding
	data. They will also be able to
	request treatment allocation
	data where necessary (e.g. for
	the purposes of preparing
	interim reports).
Blinded	Where possible the senior trial

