# 8. Trial procedures and assessments

#### 8.1. Summary of assessments

A summary of trial procedures is shown in figure 2. A detailed description of each procedure can be found in section 8.2.

Figure 2: Summary of trial procedures time point

Trial	TB-DILI Trial	Protocol	1.2	date:	02-Aug-2022	Page 30 of 58
name:		version:				

															TRIAI	L PERI	OD						
TIMEPOINTS	E	R	Pha	ise A						Pha	se B				Phase	e C		DIL	Recurrence		ЕоТ		Follow- up Post R
Timepoint [Weeks]	W-2	W-1				W0				W1	W2	W4	W6	W8	W16	W24	W32	Diagnosis	2-Weeks after	W25	W33	*	W52
Timepoint [Days]		-1	0	1	3	4	6	7	9									of DILI	treatment re-start				
Tolerance [Days]	а	±2	±1	±1	±1	±1	±1	±1	±1	±4	±4	±4	±4	±4	±14	±14	±14	-	-	-	-		-
ENROLMENT:																							
Eligibility screen	Х																						
Informed consent	Х																						
Baseline Assessments																							
Adjudication panel confirmation	Х																	Х					
EQ-5D-5L	Х																						
Randomisation		Х																					
CONTROL ARM																							
Drug Re-Introdcution																							
Reintroduce EH				Х																			
Reintroduce R						Х																	
Reintroduce Z								Х															
Drug Discontinuation																							
Discontinue Z+R														Х									
Assessments																							
LFT (suggested not mandated)			х		х		х		х	х	х	x	x	x	x	x	x	х	х				
EQ-5D-5L			Х								Х							Х	Х	Х			Х
Follow-Up post EoT																							
Follow-up telephone call																				Х		Х	
INTERVENTION ARM																							
Drug Re-Introdcution																							
Reintroduce EH				Х																			
Reintroduce R						Х																	
Drug Discontinuation																							
Discontinue R														Х									
Assessments																							
EQ.5D-5L			Х						_	Γ.	Х							Х	Х		Х		Х
Follow-Up post EoT						CI 31				_					 								
Follow-up telephone call					ľ	5.510	[														Х	Х	

E = Enrolment

R = Randomisation

EoT = End of Treatment

a. The enrolment period will occur at the onset of DILI, the period between E & R will be variable dependent upon patient recovery. Predicted average time is 2 weeks

\* Every 12 weeks after EoT until 12 months post R

Trial	TB-DILI Trial	Protocol	1.2	date:	02-Aug-2022	Page 32 of 58
name:		version:				

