#### 9.1.3.Randomisation

Upon confirmation of DILI by the adjudication panel, randomisation will occur after the patient has recovered, and the attending clinician is prepared to re-commence treatment. The Principal Investigator or delegated site staff will randomise the patient using the online randomisation system via a secure website developed and maintained by NCTU.

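### After randomisation the schedule ties blinded DILI adjudication to a diagnosis by the open-label site; no site-independent referral route is written, and the panel's verdict is not named as the primary outcome

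*Protocol*

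**What the plan says.** **Panel remit.** The Hepatic Adjudication Panel paragraph in Section 4 says: "A blinded Hepatic Adjudication Panel will review all relevant data relating to possible DILI episodes". It adds that raised enzymes alone do not establish DILI, and that timing and alternative causes must be weighed. Table 3 (Section 6.3) is equally wide. The panel stays blinded "when performing adjudication for a potential DILI during various timepoints within the trial".

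**Panel timing.** In Figure 2 (Section 8.1) the row "Adjudication panel confirmation" has two marks. One is at enrolment, for the index episode, consistent with Section 9.1.3: "Upon confirmation of DILI by the adjudication panel, randomisation will occur after the patient has recovered". The other is in the column for diagnosis of DILI during follow-up. There is none at the routine LFT visits, end of treatment or week 52. The DILI Recurrence entry in Section 9 lists only the EQ-5D-5L and stopping of the allocated regimen.

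**Who diagnoses.** Section 6.3: "Blinding of the participants and site research team following randomisation is not possible due to the nature of the interventions".

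**Data held centrally.** Section 4.2: "Sites will be requested to upload all LFTs performed onto the eCRF". Figure 2 marks LFT timing as suggested and not mandated.

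**Counting.** Section 14.2.2 compares the proportion with DILI recurrence, without saying that this is adjudicated recurrence. Participants who finish treatment with no recurrence count as event-free unless there is contrary evidence.

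**The concern.** Blinded adjudication protects an open-label outcome only if the cases reaching the panel are chosen without regard to arm. Here the one operational statement for the period after randomisation places the panel behind a diagnosis, and the site is the only party described as observing the participant. A rise that meets the laboratory criteria, but that the site attributes to something else, has no written path to the panel. Under Section 14.2.2 that participant would then count as event-free, and nobody is assigned to look for contrary evidence.

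Section 1.1 states the premise that pyrazinamide carries the higher DILI risk. A clinician who shares it could call the same rise DILI more readily in the 4-drug arm. Under-calling in the 3-drug arm would favour the intervention, and review of referred cases alone could not undo that. With few events expected, a handful of unreferred cases matters.

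**Working it through.** **Inputs from Section 14.1.1:** 10% versus 1.5% recurrence, two-sided 5%, pooled-variance Z test, 175 per arm recruited and 157 analysed, 90% power.

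**Reproducing the plan.** With p̄ = (p1 + p2)/2, SE0 = √[2p̄(1 − p̄)/n] and SE1 = √[(p1(1 − p1) + p2(1 − p2))/n], power is Φ[(|p1 − p2| − 1.96·SE0)/SE1]. At n = 157, p̄ = 0.0575, SE0 = 0.02627 and SE1 = 0.02583, so (0.085 − 0.0515)/0.02583 = 1.297 and power is 90.3%. The required size is 156 per arm, or 174 after 10% loss, against the stated 157 and 175. The plan reproduces. Expected events are 157 × 0.10 = 15.7 and 157 × 0.015 = 2.4.

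**Referral model (assumed).** The panel judges every referred case correctly, and a share s of true recurrences is referred. The observed rate is then s times the true rate. No document gives s, so the values below only show scale.

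*No true difference, under-referral in the 3-drug arm only.* The rejection rate is the sum of the product of the two binomial probabilities over all outcomes with pooled |z| > 1.96, n = 157 per arm.

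| True rate, both arms | Non-referral, 3-drug arm | Observed rates | Rejection rate |
|---|---|---|---|
| 10% | 0% | 10% v 10% | 5.1% |
| 10% | 20% | 10% v 8% | 9.4% |
| 10% | 30% | 10% v 7% | 15.6% |
| 5% | 20% | 5% v 4% | 6.9% |

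The excess is almost all in favour of the 3-drug arm. At 10% v 8%, 8.9 of the 9.4 percentage points fall on that side.

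*Design rates, equal non-referral in both arms.*

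| Non-referral | Observed rates | Power, protocol's approximation | Power, exact |
|---|---|---|---|
| 0% | 10% v 1.5% | 90% | 94% |
| 20% | 8% v 1.2% | 82% | 87% |
| 30% | 7% v 1.05% | 77% | 81% |

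For example, at 8% v 1.2%, SE0 = 0.02364 and SE1 = 0.02333, so (0.068 − 0.0463)/0.02333 = 0.928 and Φ = 0.823.

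*Design rates, 20% non-referral in the 3-drug arm only.* The observed rates are 10% v 1.2%. The risk ratio moves from 0.15 to 0.12 and approximate power from 90% to 93%. If the true effect is as large as planned, one-sided under-referral flatters the result slightly. The false-positive risk matters when the true difference is small or absent.

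**The case against.** **The panel's remit is wider than site-diagnosed cases.** Section 4 and Table 3 speak of possible and potential DILI. At enrolment the panel receives a suspected event and decides for itself whether it was DILI, and the recurrence mark in Figure 2 can be read the same way. Section 14.2.2 admits contrary evidence, and all LFTs are requested. This stands against a stronger reading that a reader might infer, namely that the panel can never add an event and that the primary count necessarily keeps the site's bias. The documents do not support that. They leave a possible route, but do not write one down or assign it to anyone.

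**Discretion over large ALT rises is limited.** Section 1.1 does say: "Not all asymptomatic increases in liver enzymes while on ATT constitute DILI episodes". It is tempting to infer that a site may freely label a rise above five times ULN as adaptation. The same paragraph goes on to treat such rises without symptoms as early DILI, and Table 1 lets them qualify alone. This stands. The discretion lies mainly in attribution to other causes, in ALP rises, and in participants with raised baseline values.

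**Details may sit in a panel charter or the SAP.** Possibly. But what triggers referral is a conduct rule that sites and the trials unit must follow during the trial, and the protocol's own schedule already gives a narrower answer than its text.

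**The rates are assumed, and equal non-referral is not differential bias.** Both are true. The power figures show a loss of information, not bias, and by exact calculation power stays above 80% even at 30%.

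**A database query cannot apply the whole of Table 1.** Symptoms and bone pathology are not LFT values. This stands and shapes the fix.

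**Conclusion.** The point holds as a gap between the panel's stated scope and its scheduled use. After randomisation the only scheduled panel review follows a diagnosis, sites are unblinded, no site-independent trigger is written, and the adjudicated verdict is not named as the primary outcome. If referral follows the site's call, adjudication corrects over-calling but not under-calling, and any difference in referral between arms enters the primary comparison.

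The size is unknown. Under one-sided non-referral of 20 to 30% and a true 10% in both arms, the nominal 5% test rejects in 9.4 to 15.6% of trials. At a true 5% in both arms, 20% non-referral gives 6.9%. Equal non-referral of 20 to 30% at the design rates costs about 8 to 14 percentage points of power by the protocol's approximation (90% to 82% or 77%). All of this rests on assumed referral rates and a panel that judges every referred case correctly. It shows what is at risk, not that bias will occur. The change is worth making because the LFT results are already requested centrally and the panel already exists.

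**What to change.** Reconcile the panel paragraph in Section 4, Table 3 and Figure 2 by stating that referral does not depend on the site's diagnosis. Then write the rule:

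1. The trials unit checks every LFT uploaded after randomisation, in both arms and without reference to allocation, against the laboratory thresholds: ALT above 3 and above 5 times ULN, ALP above 2 times ULN, and the raised-baseline rule using values from before ATT.
2. Every crossing goes to the blinded panel, together with every site-suspected episode and every treatment stop for suspected DILI.
3. The panel uses the clinical data to judge symptoms, bone pathology and alternative causes, which the LFT check cannot do.
4. Section 14.2.2 names the panel's verdict on all referred cases as the primary outcome.

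The cost is a programmed check, the queries needed to obtain clinical detail and pre-ATT values, and panel time on rises that prove not to be DILI. Treatment is unaffected. The rule cannot recover rises that were never tested or never uploaded, because LFT timing is not mandated and upload is only requested.
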